Appendix IX – Childbearing Potential & Contraception

Schema

If a patient is deemed ineligible or a does not start first dose of treatment, please refer to Section 13.0 for follow-up information.

Cycle length=28 days

NOTE: The Safety portion of this trial will monitor six patients in each arm (combination and single agent) and observe them for a minimum of 28 days to assess toxicities.

Primary & Secondary MF: Primary Myelofibrosis (PMF) and Secondary MF after Polycythemia Vera (PV) and Essential Thrombocytosis (ET) (post-PV/ post-ET MF)

Generic name: AZD1775, Adavosertib Brand name(s): n/a Availability: Provided by AstraZeneca
	
Generic name: Cytosine arabinoside Brand name(s): Cytosar, ® Availability: Commercially available

--	--

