AZD1775 dosing and cycle length: In ongoing Phase 1 solid tumor single agent AZD1775 trial at the National Cancer Institute (NCT01748825 and REFMAAL 384, see IB), current information of toxicity and tolerability supports the initial AZD1775 dosing to be 300mg QD on a 5 days on 2 day off schedule for 2 weeks every on a 21 days (3 weeks) scheduled as proposed for Arm C. For AraC there is a clinical rationale for 10 and 12 day dosing schedules if given subcutaneously. AZD1775 at 200-225mg BID x 5 doses was tolerated with full dose (strength) chemotherapy in solid tumor patients (Leijens, JCO 2016). Therefore, taken the safety and tolerability data from various studies with AZD1775, as well as our preclinical data of optimal sensitization with concurrent AraC and AZD1775 treatment, the proposed AZD1775 dose in combination with AraC is AZD1775 at 200mg once daily on a 5-2-5 schedule every 4 weeks (28 days), the latter to account and mirror the commonly used clinical s.c. AraC cycle length of 4 weeks. However, it should be noted that cycle length is often 4-6 weeks for s.c. AraC, which will be reflected in the dose adjustment and toxicity study criteria.

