4.0 Test Schedule

Table 4.1: Test Schedule for Elderly Newly Diagnosed and Relapsed/Refractory AML patients

Tests and procedures	Active Monitoring Phase					
	≤14 days prior to registration	≤7 days prior to registration	Cycle 1 Days 1, 4, 8, 15, & 28(±3 days) ^{5, 16}	Cycles 2 & 3 Days 1, 15, and 28 (± 3 days) ^{5, 16}	Cycles 4+ and Beyond Day 1 (±3 days) ^{5, 16}	EOS ₂
History and exam, wt, PS, vitals	X		X	X	X	X
Height	X					
Adverse event assessment	X		X	X	X	X
Hematology group WBC ANC Hgb PLT		X	X _A	X _B	X ₉	X
Chemistry group: sodium, potassium, calcium, creatinine, bicarbonate, glucose, chloride, albumin, BUN, alkaline phosphatase, AST, ALT, total protein, total bilirubin, LDH		X	X _A	X _B	X	X
TLS monitoring (for selected AML patients): BUN, calcium, CO ₂ , chloride, creatinine, glucose, potassium, sodium, uric acid, phosphorus			X ₁₃			
PT/PTT and D-dimer			X ₁₈			
Serum pregnancy test ₁		X		X	X	
Bone marrow biopsy and aspirate procedure (cytogenetics or FISH) ¹⁴	X ₁₁		X ₃	X ₃	X ₃	X ₁₀
Bone marrow aspirate research specimens (see Section 14.0) _R	X ₈		X ₇	X ₇	X ₇	X ₆
Blood specimens (see Section 14.0) _R	X _{4, 8}		X ₄	X ₄	X ₄	X ₄

Saliva Sample, see Section 14.0) ^R	X					
Patient Questionnaire Booklet ¹²	X		X ₁₅	X ₁₅	X ₁₅	X ₁₅
ECG (12 lead) ¹⁷		X	X _C	X	X	X

1. For women of childbearing potential only. Day 1 of each cycle
2. 30 days (+/-3days) post last dose of study drug
3. For AML patients: marrow aspirates and biopsies will be done after cycle 1 (at physician's discretion), after cycles 2 and 4, and then at physician discretion). In addition, bone marrow should be performed at time of suspected CR/CRi and/or disease progression and at physician discretion as clinically indicated. Note: Bone Marrow Aspirate and biopsy may be avoided after cycle 4 as determined by study chair or treating physician (i.e. if determined to not yield information that would change clinical management).
4. Blood specimens for research sampling to be collected as defined in Section 14.
5. Day 1 assessments do not need to be repeated if pre-registration or Day 28 assessments completed within 72 hours of Day 1.
6. Only if an EOS marrow sample is collected as part of standard of care
7. Research bone marrow samples are to be collected at the same time when a marrow is done as part of patient's standard of care, including research marrow samples should be drawn at time of marrow for suspected CR/CRi and/or disease progression.

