Table 4.2: Test Schedule for HMA failure MDS/ AML patients

Tests and procedures	Active Monitoring Phase					
	≤14 days prior to registration	≤7 days prior to registration	Cycle 1 Days 1, 8, 15, & 28(± 3 days) ^{12, 10}	Cycle 2 Days 1, 15, and 28 (± 3 days) ^{10, 12}	Cycles 3+ and Beyond Day 1 (±3 days) ^{10, 12}	EOS ₂
History and exam, wt, PS, vitals	X		X	X	X	X
Height	X					
Adverse event assessment	X		X	X	X	X
Hematology group WBC ANC Hgb PLT		X	X	X	X	X
Chemistry group: sodium, potassium, calcium, creatinine, bicarbonate, glucose, chloride, albumin, BUN, alkaline phosphatase, AST, ALT, total protein, total bilirubin, LDH		X	X _A	X _B	X	X
Serum Erythropoietin level	X					
Serum pregnancy test ¹		X		X	X	
Bone marrow biopsy and aspirate procedure (cytogenetics or FISH ⁹)	X ₆			X ₃	X ₃	X ₇
Blood specimens (see Section 14.0) _R	X _{4,13}		X ₄	X ₄	X ₄	X ₄
Saliva Sample (see Section 14.0) _R	X					
Bone marrow aspirate research specimens (see Section 14.0) _R	X _{6, 13}			X ₅	X ₅	X ₅
Patient Questionnaire Booklets ⁸	X				X ₈	X
ECG (12 lead) ¹¹		X	X _C	X	X	X

1. For women of childbearing potential only Day 1 of each cycle
2. 30 days (+/-3days) post last dose of study drug
3. Marrow biopsies only to be done at End of cycle 2, End of cycle 4, at time of suspected CR/CRi and thereafter at physician discretion as clinically indicated (i.e. disease progression).

4. Blood specimens for research sampling to be collected as defined in Section 14.
5. Research marrow samples (aspirates) to be done at times of clinical standard of care marrow tests at End of cycle 2, End of cycle 4, at time of suspected CR/CRi or disease progression and thereafter at physician discretion as clinically indicated. A sample will be obtained at end of study (EOS) if a bone marrow is performed as part of patient's standard of care; sample will be collected per section 14.0
6. ≤ 28 days prior to registration; for patients with an outside marrow biopsy within 4 weeks of study start, outside results can serve as baseline after review at NYU.
7. Bone marrow at end of study is only to be done at physician discretion and is optional. Progression marrow can be used as EOS marrow if patient is taken off trial based on the results.

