6.3 Safety & Expansion Portions

6.31 Correlative Research

6.311 A mandatory correlative research component is part of this study, the subject will be automatically registered onto this component (see Section 3.17 and 14.0).

6.32 At the time of registration, the following will be recorded:

- Subject has/has not given permission to store and use his/her sample(s) for future research of Acute Myeloid Leukemia or Myelodysplastic Syndrome at NYU Langone Health.
- Subject has/has not given permission to store and use his/her sample(s) for future research to learn, prevent, or treat other health problems.
- Subject has/has not given permission to give his/her sample(s) to researchers at other institutions.

6.33 Treatment on this protocol must commence at a participating institution, NYU Langone Health, under the supervision of a hematologist.

6.34 Treatment cannot begin prior to registration and must begin \leq 14 days after registration.

- 6.35 Pretreatment tests/procedures (see Section 4.0) must be completed within the guidelines specified on the test schedule.
- 6.36 All required baseline symptoms (see Section 10.3) must be documented and graded.
- 6.37a Study drug is available on site.
- 6.37b Blood draw kit is available on site.
- 6.37c Subject questionnaire booklet is available on site; copies are not acceptable for this submission.
- 6.37d Randomization Procedures
- 6.37d1 After the subject has been registered into the study, the values of the grouping factors will be recorded. An elderly newly diagnosed AML subject will be allocated to arm A. A relapsed/refractory AML or HMA failure MDS/ AML subject will be randomized to treatment group arm B or arm C. MF patients will be allocated to Arm C but not included in the statistical analysis for Arm C, rather descriptive response rates will be summarized separately.
- Elderly (age 60+) newly diagnosed AML subjects assigned to Arm A: AZD1775 days 1-5, 8-12 and AraC days 1-5, 8-12
 - Relapsed/Refractory AML and HMA failure MDS/ AML subjects randomized to Arm B: AZD1775 days 1-5, 8-12 and AraC days 1-5, 8-12 or Arm C: AZD1775 days 1-5, 8-12.
 - MF patients allocated to Arm C

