7.3 Treatment Plan for AZD1775 single agent (Arm C)

7.31 Safety Portion

The Safety portion of this trial will treat and monitor up to six subjects in the arm and observe them for a minimum of 21 days to assess toxicities. The Safety portion will first treat 3 patients at a single dose AZD1775 of 300mg daily (dose level 0) on days 1-5 and 8-12 for 21 days. If 0/3 patients experience DLT, another 3 patients will be treated. If \leq 1/6 patients have DLT, 300mg will be the tolerated dose (MTD) and advanced to the Expansion portion of the study. If \leq 2/6

patients have DLT, dose will be de-escalated to dose level -1 (AZD1775 250mg daily on days 1-5 and 8-12 for 21 days) and 3 patients treated. If $\leq 1/3$ patients have DLT another 3 patients will be treated. If $\leq 1/6$ patients have DLT, 250 mg AZD1775 will be the tolerated dose (MTD) and advanced to the Expansion portion of the study. If $\leq 2/6$ patients have DLT at dose level -1 (250 mg AZD1775) dose will be further de-escalated to dose level -2 (AZD1775 200mg daily on days 1-5 and 8-12 for 21 days) and 3 patients treated. If $\leq 1/3$ patients have DLT another 3 patients will be treated. If $\leq 1/6$ patients have DLT, dose level -1 (200 mg AZD1775) will be the tolerated dose (MTD) and advanced to the Expansion portion of the study. If $\leq 2/6$ patients have DLT at dose level -2 (200 mg AZD1775) dose will be further de-escalated to dose level -3 (AZD1775 150 mg daily on days 1-5 and 8-12 for 21 days) and 3 patients treated. If $\leq 1/3$ patients have DLT another 3 patients will be treated. If $\leq 1/6$ patients have DLT, dose level -3 (150 mg AZD1775) will be the tolerated dose (MTD) and advanced to the Expansion portion of the study. If $\leq 2/6$ patients have DLT at dose level -3 (150 mg AZD1775) **or** if $\geq 2/6$ patients experience DLT at any dose level, then enrollment into that dose level will be placed on hold, and a meeting of all participating investigators, the NYU DSMC Medical Monitor, the Astra Zeneca Trial/ Program Lead will be called to determine how best to proceed, as well as available PK data will be reviewed.

Table 7.31 Single agent AZD1775 (Arm C)

Dose	AZD1775 ¹
0	300 mg PO once daily days 1-5 & 8-12 every 21 days
-1	250 mg PO once daily days 1-5 & 8-12 every 21 days
-2	200 mg PO once daily days 1-5 & 8-12 every 21 days
-3	150 mg PO once daily days 1-5 & 8-12 every 21 days

¹AZD1775 should be taken either 2 hours before or 2 hours after a meal.

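### Routine response marrows are timed by cycle, but the randomised arms have different cycle lengths (28 days in B, 21 in C), so scheduled looks fall on days 56/112 v 42/84

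*Combined protocol and SAP*

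**What the plan says.** Section 6.37d1: "A relapsed/refractory AML or HMA failure MDS/ AML subject will be randomized to treatment group arm B or arm C". Section 16.23 compares these arms on CR/CRi with 20 evaluable patients each. An arm shows efficacy with at least 3 responses. If both do, the combination is preferred when its rate is at least 10 points higher.

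Routine marrows are counted in cycles. Table 4.2, footnote 3: "Marrow biopsies only to be done at End of cycle 2, End of cycle 4, at time of suspected CR/CRi", then at discretion. Table 4.1, footnote 3 (AML): "after cycles 2 and 4, and then at physician discretion", with an optional marrow after cycle 1 and marrows at suspected CR/CRi or progression. Neither footnote gives a calendar day or distinguishes the arms.

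Cycle length differs by arm. Table 7.22 repeats the combination every 28 days, and Section 1.51 agrees: "AZD1775 at 200mg once daily on a 5-2-5 schedule every 4 weeks (28 days". For Arm C, Table 7.31 has "300 mg PO once daily days 1-5 & 8-12 every 21 days", Section 7.32 repeats 21 days, and Section 1.51 has "21 days (3 weeks) scheduled as proposed for Arm C".

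Two places imply 28 days for everyone. The Schema states "Cycle length=28 days" with no arm distinction, and the cycle 2 column of Table 4.2 reads "Days 1, 15, and 28 (± 3 days". A 21-day cycle has no Day 28.

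**The concern.** CR/CRi cannot be declared without a marrow (Sections 11.1 and 11.2). If the routine marrow falls earlier in one randomised arm, part of the observed difference can come from the calendar. A response that develops between days 84 and 112 can be caught by a routine look in Arm B but not in Arm C. A patient who has responded but leaves between days 42 and 56 can be caught by a routine look in Arm C but not in Arm B.

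The comparison is sensitive to small shifts: 10 points on 20 patients is 2 responses. The operating characteristics in Section 16.23 take the tabulated rates as observed, so they assume equal ascertainment. Section 16.44 measures time to response and time to progression from registration to first documentation, so these inherit the schedule directly.

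**Working it through.** **Scheduled days** (cycle number × cycle length, before delays and windows, taking Section 7 as governing)

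| Routine marrow | Arm B | Arm C | Gap |
|---|---|---|---|
| End of cycle 2 | 2 × 28 = 56 | 2 × 21 = 42 | 14 days |
| End of cycle 4 | 4 × 28 = 112 | 4 × 21 = 84 | 28 days |

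If the Schema's 28 days applied to both arms, both would be at 56 and 112 and the gap would vanish.

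**The plan's own figures.** With n = 20 per arm and independent binomials, the combination is selected if B has at least 3 responses and either C has fewer than 3 or B leads by at least 2. For true rates (C, B), this gives 0.070 at (0.05, 0.05), 0.300 at (0.25, 0.25), 0.442 at (0.20, 0.25), 0.607 at (0.15, 0.25), 0.769 at (0.10, 0.25) and 0.881 at (0.05, 0.25). All match the table in Section 16.23 after rounding.

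**Without a response-time model.** Assume both arms are truly 25% and Arm C's observed rate is lowered by a relative 5/10/15/20%. The combination is then selected with probability 0.33/0.37/0.40/0.44 instead of 0.30. Arm C meets its own 3-of-20 rule with probability 0.89/0.86/0.83/0.79 instead of 0.91.

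**With assumed response times.** The documents give no distribution. Assume a true 25% in both arms and log-normal time to response with median m and log-SD 0.5. Let F(t) = Φ[(ln t − ln m)/0.5] be the share of responses reached by day t, and r the share of later responses found by triggered or discretionary marrows. The observed rate is 0.25 × [F(t) + r(1 − F(t))], with t = 84 in C and 112 in B.

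| m (days) | F(84), F(112) | C v B, r = 0 | P(select combination), r = 0 | r = 0.5 | r = 0.8 |
|---|---|---|---|---|---|
| 45 | 0.894, 0.966 | 22.4% v 24.2% | 0.35 | 0.32 | 0.31 |
| 60 | 0.750, 0.894 | 18.7% v 22.4% | 0.41 | 0.35 | 0.32 |
| 75 | 0.590, 0.789 | 14.7% v 19.7% | 0.46 | 0.37 | 0.33 |

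**Adding dropout.** Keep r = 0 and add exponential dropout with a 60-day median (assumption), S(t) = exp(−t ln 2/60). A response counts only if the patient is still on study at the next routine marrow. With looks at t1 and t2, the observed rate is 0.25 × {F(t1)S(t1) + [F(t2) − F(t1)]S(t2)}.

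| m (days) | C (42, 84) | B (56, 112) |
|---|---|---|
| 30 | 13.7% | 12.4% |
| 45 | 11.1% | 10.8% |
| 60 | 8.5% | 8.9% |
| 75 | 6.3% | 7.1% |

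Fast response with early dropout favours C; slow response favours B. The sign depends on quantities the documents do not give.

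**Time-to-event endpoints.** For an event first found at the first routine marrow, the dates differ by 56 − 42 = 14 days for the same underlying course.

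**The case against.** Marrows at suspected CR/CRi stand in the same footnotes, Section 16.21 has blood-based response assessment at cycle ends, and shorter cycles give Arm C more such looks per month. CR/CRi counts over all cycles, Section 11.0 sets no maximum number of cycles, and the last patient is observed for at least 4 months. All of this stands, and it is why the r = 0 column is a worst case. A reader might infer that the endpoint is measured only on days 42/84 and 56/112, or that the schedule favours the combination. The documents support neither: those are only the routine looks, and the dropout table shows the direction can reverse.

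The softening is incomplete. CRi is defined by persistent neutropenia or thrombocytopenia, so blood counts are a weak trigger for that part of the endpoint. Suspicion is a physician's judgement, and no blinding is described. Table 4.1 lets marrows be avoided after cycle 4, which is day 84 in C and day 112 in B. Section 11.0 itself anticipates unconventional response kinetics.

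Cycle counting can be defended as exposure matching: with 10 AZD1775 dosing days per cycle, both arms have 20 before the first look and 40 before the second. But it gives the arms different time at risk of a documented response, and Section 16.44 counts calendar time from registration.

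Finally, Section 16.1 disclaims a definitive superiority conclusion, differences below 10 points allow other factors to decide, and no B-versus-C test of time to response is planned. This limits the consequence. It does not remove the effect from a selection that can turn on 2 responses.

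**Conclusion.** The point holds in a limited form. Under the cycle lengths in Section 7, routine response marrows in the two randomised arms are 14 days apart at the first look and 28 at the second. The effect on the CR/CRi comparison is probably modest, and neither its size nor its sign can be derived from the documents. With both arms at 25%, assumed log-normal response times and no dropout, selection of the combination moves from 0.30 to 0.35–0.46 if nothing is detected after the last routine marrow, and to 0.32–0.37 if half of late responses are found. With early dropout the shift can favour Arm C. Time to response and time to progression are affected more directly, by 14 days, but only for events first found at the first routine marrow.

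The Schema's 28-day cycle and the Day 28 columns do not settle the matter. They contradict the Arm C treatment tables, and that inconsistency needs reconciling separately; by itself it does not show endpoint bias. Severity: should be fixed, not a critical defect.

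**What to change.** In Tables 4.1 and 4.2, time the routine response marrows for Arms B and C by common weeks from first dose with a common window, for example weeks 8 and 16 ± 7 days (days 49–63 and 105–119). Keep two routine marrows and the marrows at suspected CR/CRi or progression.

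If marrows stay at cycle ends, Arm B is sampled after cycles 2 and 4 (days 56, 112) and Arm C after cycles 3 and 5 (3 × 21 = 63, 5 × 21 = 105). The gap is then 7 days at each look instead of 14 and 28; marrows taken on the target day in both arms would close it. With r = 0, no dropout and t = 105 for Arm C, P(select combination) for m = 45/60/75 is 0.31/0.32/0.33, close to the designed 0.30.

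Separately, reconcile the Schema's cycle length and the Day 28 columns in Tables 4.1–4.3 with the 21-day Arm C cycle in Section 7.3, so that sites can schedule Arm C from one consistent text.

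The cost is footnote and column edits, with no extra routine marrow. The downside is that the first routine Arm C marrow moves later, from day 42 to as late as day 63, unless response or progression is suspected sooner.

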1.41 Clinical Safety

Several clinical studies with AZD1775 alone and in combination with (mostly full dose) cytotoxic chemotherapy have been conducted.

The RP2D of AZD1775 monotherapy has been established as 300mg QD day1-5, and 8-10 in week 1 and 2 of a 3 week schedule.

The MTDs of AZD1775 when administered with chemotherapy are presented in the table below:

Maximum-tolerated doses of AZD1775 when administered in combination with chemotherapy

Chemotherapy	Dose Frequency	AZD1775 (mg)
Gemcitabine 1000 mg/m ² on Day 1 weekly for 3 consecutive weeks out of every 4 weeks	Single-dose	200
Cisplatin 75 mg/m ² on Day 1 every 21 days	Single-dose	200
Carboplatin AUC 5 on Day 1 every 21 days	Single-dose	325
Gemcitabine 1000 mg/m ² on Day 1 weekly for 3 consecutive weeks out of every 4 weeks	Multi-dose	175 QD x2 days

Cisplatin 75 mg/m ² on Day 1 every 21 days	Multi-dose	200 BID x 2.5 days
Carboplatin AUC 5 on Day 1 every 21 days	Multi-dose	225 BID x 2.5 days

BID = twice daily; QD = once daily

Based on the safety data from the completed AZD1775 clinical studies and preliminary data from ongoing studies adverse drug reactions to AZD1775 monotherapy include: anaemia, neutropenia, thrombocytopenia, QTc prolongation, gastrointestinal events such as dyspepsia, diarrhoea, nausea and vomiting (with or without dehydration or serum electrolyte decreases), as well as decreased appetite. In addition, the following events are also considered expected during treatment with AZD1775 in combination with cytotoxic chemotherapy: febrile neutropenia, leukopenia, stomatitis, asthenia, fatigue, mucosal inflammation and myalgia.

Based on information emerging during the clinical development programme of AZD1775, potential risks where a causal relationship with AZD1775 monotherapy has not been established include asthenia/fatigue, febrile neutropenia, gastrointestinal haemorrhage, lymphopenia/lymphocyte count decreased, leukopenia/WBC count decreased, myalgia, stomatitis, sepsis and transaminases elevation.

In addition, the following events are also considered potential risks for AZD1775 in combination with cytotoxic chemotherapy: tachycardia and pancytopenia.

Refer to the IB for AZD1775 for information on the potential benefits and assessment of potential and known risks.

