8. Patient questionnaire booklet must be used; copies are not acceptable for this submission. Booklet should be completed by patient prior to review of treatment response and discussions of patient's general health since last treatment evaluation. Booklets to be completed at baseline, cycles 3, 6, 9, and EOS.
9. Either conventional cytogenetics or FISH panel (or both based on physician discretion) for MDS should be performed at baseline. If diploid cytogenetics at baseline subsequent cytogenetic studies may be omitted unless disease progression is suspected. For FISH based cytogenetic assessments, an entire MDS FISH panel should be performed at baseline, while on subsequent marrows only positive specific FISH abnormalities/probes need to be repeated unless disease progression is suspected.
10. Prior to the start of treatment.
11. ECG in triplicate on day1 of each cycle,
12. Day 1 assessments do not need to be repeated if pre-registration or Day 28 assessments completed within 72 hours of Day 1.
13. To be collected on all patients at baseline. If no baseline marrow samples obtained, the peripheral blood research sample becomes mandatory to participate in study. If collected bone marrow aspirate specimens must be collected and submitted per section 14.0. If bone marrow performed at end of study as part of patient's standard of care, collect bone marrow sample per section 14.0.
 - A For AML patients, CBC and blood chemistries will be collected at least twice weekly for Cycle 1. TLS labs will be performed at least twice during the first week of therapy
 - B For AML patients, CBC and blood chemistries will be collected weekly for Cycle 2
 - C For cycle 1, ECGs will be conducted at least weekly.
 - R Research funded (see Section 19.0).

Table 4.3: Test Schedule for MF patients

Tests and procedures	Active Monitoring Phase					
	≤14 days prior to registration	≤7 days prior to registration	Cycle 1 Days 1, 15, & 28(± 3 days) ^{12, 10}	Cycle 2 Days 1, 15, and 28 (± 3 days) ^{10, 12}	Cycles 3+ and Beyond Day 1 (±3 days) ^{10, 12}	EOS ²
History and exam, wt, PS, vitals	X		X	X	X	X
Height	X					
Adverse event assessment	X		X	X	X	X
Hematology group WBC ANC Hgb PLT		X	X	X	X	X
Chemistry group: sodium, potassium, calcium, creatinine, bicarbonate, glucose, chloride, albumin, BUN, alkaline phosphatase, AST, ALT, total protein, total bilirubin, LDH		X	X	X	X	X
Serum Erythropoietin level	X					
Serum pregnancy test ¹		X		X	X	

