7.33 Hydroxyurea (HU)

For patients randomized to Arm C single agent AZD1775, HU may be added after the first cycle of therapy at the physicians discretion after discussion with the PI. HU dose should be started according to clinical judgement at 500-1000mg/ day and titrated for additional myelosuppression as needed. Note: for patients with Myelofibrosis, HU can be given during cycle 1 at the previously tolerated dose.

7.4a Toxicity Assessment for Safety Portion: DLT definition and RP2D

Toxicity will be measured per NCI-CTCAE version 5.0. DLT is defined as an adverse event occurring during the first cycle of treatment that is not clearly related to the subject's underlying disease and that meets one of the following:

- Grade 3 or higher toxicity as per NCI Common Terminology Criteria for Adverse Events (CTCAE) version 5.0 not clearly resulting from the underlying leukemia and that does not resolve to \leq Grade 2 within 24 hours with the following exceptions;
 - Grade 3 fatigue, asthenia, fever, anorexia, or constipation;
 - Grade 3 nausea, vomiting or diarrhea not requiring tube feeding, total parenteral nutrition, or requiring or prolonging hospitalization;
 - infection, bleeding or other expected direct complication of cytopenias due to active underlying disease;
 - Grade 3 or 4 tumor lysis syndrome (TLS) if it is successfully managed clinically and resolves within 7 days without end-organ damage;
 - Grade 3 or 4 isolated electrolyte abnormalities that last < 72 hours.
- Grade 3 AST, ALT or alkaline phosphatase will be considered dose limiting if it last > 72 hours
- treatment-related deaths are dose limiting
- confirmed Hy's law cases are dose limiting

NOTE: Myelosuppression will not be considered in evaluating toxicity in subjects with acute leukemias or similar advanced myeloid malignancies (MDS, MF) except where bone marrow (BM) hypoplasia occurs for >42 days with BM cellularity <5% in the absence of residual leukemia/disease.

7.4.b RP2D for the combination of AZD1775 with Cytarabine; DLT, MTD and Biological dose

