In this case, a written statement outlining drug dosage, method of administration, follow-up tests required, and telephone number to call to discuss any questions with the responsible investigator must be sent with the patient to provide necessary information to the LMD, post cycle 1 of treatment therapy. The LMD will be required to supervise the administration of the study drugs as stipulated in the protocol and provide written documentation that the drug was administered.

8.0 Dosage Modification Based on Adverse Events - If multiple adverse events are seen, administer dose based on greatest reduction required for any single adverse event observed. Dose modifications apply to the treatment given in the preceding cycle and are based on adverse events observed since the prior dose. Dose modification recommendations listed below are general guidelines, and appropriate dose adjustments for patient safety should be done if needed per treating physician discretion.

ALERT: ADR reporting may be required for some adverse events. See Section 10.0.

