Blood and Lymphatic System Disorders	Febrile neutropenia \geq Grade 3	AZD1775	May omit dose until fever has resolved or returned to baseline. Dose to be restarted at same dose level or treating physician may discuss possible dose reduction (per Table 8.12) with the Study Chair. If clinical benefit is derived, AZD1775 may be continued if the infection is managed and controlled with appropriate medical intervention (i.e. antibiotics) and the patient is felt to derive benefit from the treatment with AZD1775 (Rationale: AML, MDS and MF patients may have persistent and/ or prolonged neutropenia and will only recover if underlying disease is adequately treated].

→ → Use the NCI Common Terminology Criteria for Adverse Events (CTCAE) version 5.0* unless otherwise specified ← ←			
CTCAE System/Organ/Class (SOC)	ADVERSE EVENT	AGENT	ACTION**
Investigations	Neutrophil & Platelet count decrease ≥ grade 4 NOTE: only applicable for patients with absolute neutrophil count (ANC) of ≥ 1000mm ³ and platelet count ≥ 100,000/mm ³ at baseline (i.e. MDS or MF patients)	AZD1775	Omit dose until ANC and/or platelets have recovered to ≤ grade 2. If clinical benefit is derived, AZD1775 may be continued if not recovered to ≤ grade 2 after discussion of treating physician and study chair. For a second event reduce by 1 dose level (Table 8.12) For a third event discontinue from treatment. [If clinical benefit is derived, AZD1775 may be continued per physician assessment and after discussion with Study Chair and Medical Monitor (NYU DSMC)]
Investigations	Creatinine increased Grade 2	AZD1775	Omit dose until resolved to ≤ grade 1, then: 
 • If resolved in ≤ 7 days, then maintain dose level • If resolved in > 7 days, then decrease by 1 dose level (Table 8.12) [If clinical benefit is derived, AZD1775 may be continued if the renal function is elevated but stable]
		AraC	Continue treatment at current dose level
	Creatinine increased Grade 3 and 4	AZD1775	Omit dose until resolved to ≤ grade 1, then decrease dose by 1 dose level
		AraC	Omit dose until resolved to ≤ grade 1, then decrease dose by 1 dose level
Investigations	Blood bilirubin increased ≥ Grade 3	AZD1775	Omit dose until resolved to ≤ grade 1, then: 
 • If resolved in ≤ 7 days, then maintain dose level • If resolved in > 7 days, then decrease by 1 dose level
		AraC	Continue treatment at next lower dose level

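### Table 4.3 schedules no on-treatment blood count or chemistry for MF patients in cycle 1 before Day 15 ±3, so Table 8.32 has no scheduled laboratory result to act on before the second dosing week (cheap safety improvement)

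*Combined protocol and SAP*

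**What the plan says.** **Treatment.** Section 6.37d1 states that "MF patients will be allocated to Arm C". Table 7.31 gives the Arm C starting regimen as "300 mg PO once daily days 1-5 & 8-12 every 21 days". Sections 6.0 and 6.37d1 keep the 7 MF patients out of the Arm C analysis and summarise them separately.

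**Monitoring.** The cycle 1 column of Table 4.3 is headed "Cycle 1 Days 1, 15, & 28(± 3 days"). Hematology and chemistry are each marked with a plain X and no frequency footnote. Footnote 10 places the assessments before treatment starts, and footnote 12 lets recent pre-registration results stand in for Day 1. Table 4.2 covers HMA-failure MDS/AML patients, who may be randomized to the same Arm C regimen. Its cycle 1 column is "Cycle 1 Days 1, 8, 15, & 28(± 3 days"). The extra cycle 1 blood counts and chemistries in the footnotes to Tables 4.1 and 4.2 are for AML patients only.

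**Laboratory rules.** Table 8.32 advises omitting AZD1775 for:
- creatinine of grade 2 or higher;
- bilirubin of grade 3 or higher;
- ALT/AST of grade 3 or 4;
- a grade 4 neutrophil or platelet fall.

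The count rule is limited to patients with ANC of at least 1000 and platelets of at least 100,000 "at baseline (i.e. MDS or MF patients"). The notes under the table treat omission as a within-cycle action and illustrate it with a dose omitted on Day 8. Section 8.0 adds the qualification "Dose modification recommendations listed below are general guidelines", subject to physician discretion.

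**The concern.** A Day 8 decision to give or omit AZD1775 on laboratory grounds needs a laboratory result. For MF patients the schedule supplies none between the start of treatment and the end of the second dosing week. Changes at the Table 8.32 grades can be silent, so asking about adverse events at a contact may not prompt a test.

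The case is strongest for blood counts. Section 1.41 says that "adverse drug reactions to AZD1775 monotherapy include: anaemia, neutropenia, thrombocytopenia", and Section 7.33 adds that "for patients with Myelofibrosis, HU can be given during cycle 1 at the previously tolerated dose". It is weaker for chemistry. Section 1.41 lists transaminase elevation only as a potential risk and does not list creatinine or bilirubin. It does list QTc prolongation and gastrointestinal events that may come with electrolyte falls, and Table 8.31 ties resumption after mild QTc prolongation to electrolyte correction.

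At stake is whether a qualifying abnormality is seen before five more doses are taken.

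**Working it through.** There is no plan figure to reproduce. The check sets the visit calendar against the dosing calendar, assuming doses are taken on their nominal days.

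**Inputs**
- Dosing days 1-5 and 8-12: 5 + 5 = 10 doses in cycle 1 (Table 7.31).
- First scheduled on-treatment draw: Day 15 ±3, which is Day 12 to Day 18 (Table 4.3). Read literally, Day 1 ±3 could reach Day 4, but footnote 10 places it before treatment.
- MF cohort: 7 patients (Section 6.0), so 7 × 5 = 35 week-2 doses.
- Existing research and pharmacokinetic visit: Day 5 ±1, which is Day 4 to Day 6 (Table 14.1).

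**Doses already taken when blood is drawn before that day's dose**

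| Draw day | Doses taken, of 10 | Week-2 doses taken, of 5 |
|---|---|---|
| 4 | 3 | 0 |
| 5 | 4 | 0 |
| 6 to 8 | 5 | 0 |
| 11 | 8 | 3 |
| 12 (earliest under Table 4.3) | 9 | 4 |
| 13 to 18 (includes nominal Day 15) | 10 | 5 |

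**Results under the plan**
- Time from first dose to first scheduled result: 15 − 1 = 14 days nominal; range 12 − 1 = 11 to 18 − 1 = 17 days.
- Week-2 doses taken before that result, over the cohort: 7 × 5 = 35 of 35 at nominal Day 15; 7 × 4 = 28 of 35 at the earliest.
- Scheduled on-treatment results available before the Day 8 dose: 0.

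**With the added draw.** Any draw from Day 4 to Day 8 pre-dose, reviewed before dose 6, puts all 35 week-2 doses after a reviewed result. A ±3 window around Day 8 would not do this, because it permits Day 11, after 8 doses.

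**Illustration only.** The documents give no rate of qualifying laboratory events by Day 8. Let p be an assumed per-patient probability. Expected patients affected = 7p; chance of at least one = 1 − (1 − p)^7; upper bound on week-2 doses taken under an unseen trigger = 35p.

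| p | 7p | 1 − (1 − p)^7 | 35p (upper bound) |
|---|---|---|---|
| 2% | 0.14 | 13% | 0.7 |
| 5% | 0.35 | 30% | 1.75 |
| 10% | 0.70 | 52% | 3.5 |
| 20% | 1.40 | 79% | 7.0 |

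The last column is a bound, not a forecast. It supposes that the trigger is present before dose 6, lasts through all five week-2 doses and is not found by an unscheduled test.

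**The case against.** The strongest reply is that the gap is only in scheduled tests and that the plan treats early cytopenia lightly in these diseases.

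- **Discretion.** The dose rules are guidelines and unscheduled tests are not barred. Table 8.32 also lets AZD1775 continue for patients with clinical benefit, with stable raised creatinine or, after discussion with the study chair, with unrecovered counts. This stands. A reader might infer that MF patients go unmonitored, or that Table 8.32 cannot be applied to them. The documents support neither reading.
- **Low concern about counts.** Section 1.52 calls cytopenias less of a concern here, Section 7.4a largely excludes myelosuppression from dose-limiting toxicity, and hydroxyurea in cycle 1 is held to a dose already tolerated. Section 1.51 describes the single-agent schedule as well tolerated. This lowers the importance of the point. It does not explain a count rule that names MF with no scheduled count to feed it.
- **Other sections may imply a test.** Section 10.8 lists neutrophils, platelets, AST and ALT for grading at each evaluation, but does not define an evaluation. Section 14.4 ties research blood to routine clinical draws and to marrow procedures. Neither adds a safety blood count or chemistry to cycle 1 for MF, though in practice some sites may already take one near Day 5.
- **The comparison with Table 4.2.** Its Day 8 visit also carries ±3 days, so it does not guarantee a result before week 2 either. This stands. Table 4.2 shows only that a draw around Day 8 is already in use for this regimen, not that Table 4.3 breaches a standard kept elsewhere.
- **Unanchored rates.** The 2% to 20% range has no source in the documents. This too stands, so the conclusion rests on the calendar alone.

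**Conclusion.** The point holds as a cheap safety improvement of modest importance. In cycle 1, MF patients have no scheduled on-treatment hematology or chemistry until 9 or 10 of 10 doses have been taken. On scheduled data, the laboratory omission guidelines can therefore change at most one cycle 1 dose per patient, and only if a Day 12 pre-dose result is back the same day.

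This rests on doses being taken on their nominal days and on no other section adding a draw; none was found. For the count rule it applies only to patients with adequate baseline counts. The creatinine, bilirubin and ALT/AST rules have no such limit.

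A reader might take the 35 unreviewed week-2 doses as doses given in error, or as a measure of harm. They are neither. The figure counts process, and without an event rate the number of doses that should have been omitted cannot be estimated. Nor does the gap reach the trial's inference: the 7 MF patients are outside the Arm C analysis, so no estimate, error rate or decision rule changes.

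**What to change.** In cycle 1 of Table 4.3, add one hematology and chemistry draw at any time from the existing Day 5 (±1) pharmacokinetic and research visit up to Day 8 pre-dose. State that the result is reviewed, and the patient told to take or omit, before the Day 8 dose (dose 6). Do not apply the table's ±3 days to this draw.

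Sites can choose how to do it. The tubes can be taken at the pharmacokinetic visit, which leaves time for the result but comes after only 3 to 5 doses. Alternatively they can be taken with the week-2 ECG if that is done before the Day 8 dose; footnote 11 requires weekly cycle 1 ECGs without fixing the day. This reflects all five week-1 doses, but a Day 8 draw needs a same-day result. Either way no new visit is required. Table 8.32 and its discretion stay as they are.

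The cost is one routine blood count and chemistry per MF patient, 7 in all. Section 22.1 charges such tests to subjects, so the amendment should state who pays for this one.
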